9.2.2 Progression-free Survival

Progression-free survival (PFS) is defined as the time from first dose of rucaparib to the date of first objective evidence of progression documented by the investigator per RECIST v1.1 or death due to any cause, whichever occurs first, plus 1 day. Patients without a documented event of progression will be censored on the date of their last adequate post-baseline tumor scan or date of first dose of study drug if no tumor scans have been performed. If a patient discontinues study drug due to something other than PD and subsequently begins another anti-cancer therapy (ACT) prior to a PFS, that patient will be censored at the last tumor scan prior to the start of ACT. However, PFS events occurring more than 90 days after discontinuation of study drug, but prior to start of subsequent ACT, will not be included in

the analysis and such patients will be censored at their last scan prior to the end of the 90-day window.

PFS will be summarized in a Kaplan-Meier plot; however in the case of a low censoring rate, it may be summarized with descriptive statistics.

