1.4 Rationale for this Study of Rucaparib

Patients with MIBC represent a population with advanced disease, poor prognosis, and unmet need. The median OS in this patient population is 15 months. Response rates to initial treatment with cisplatin-based chemotherapy range from 49% to 72%; however, most patients will have disease relapse within 9 months following initial treatment.^{4,5} Furthermore, the majority of patients will progress within 2 to 3 months following failure on first- and/or second-line therapy.⁶ There are limited treatment options beyond first- or second-line treatment with platinum-containing chemotherapy and/or an immune checkpoint inhibitor, therefore additional therapies for the treatment of patients with MIBC beyond first- or second-line are needed. Treatment within clinical studies is considered an appropriate treatment option for these patients.¹⁸

Homologous recombination pathway defects may be responsible for the genetic instability observed in many cancers including ovarian cancer and urothelial cancer. For ovarian cancer, it is estimated approximately 50% of high-grade serous ovarian cancer patients have alterations in HRR genes.⁴¹ Clinical data with rucaparib have shown patients with and without a BRCA (germline or somatic) mutation benefit from rucaparib treatment in both the treatment and maintenance settings of ovarian cancer.^{16,31} While patients with a BRCA

mutation derived the most benefit, patients without evidence of a BRCA mutation also derived significant benefit suggesting an incomplete understanding of biomarkers involved in sensitivity to a PARP inhibitor.¹⁶ Similar to ovarian cancer, an analysis of TCGA bladder cancer data set (<http://cancergemone.nih.gov>) indicates that approximately 60% of bladder cancer tumors may have alterations in HRR genes and/or other genomic/epigenetic deficits that can drive HRD (Clovis, data on file). The presence of HRD in tumors has been demonstrated to predict response to cisplatin-based chemotherapy in bladder cancer.^{10,11} Based on these analyses and data, bladder cancer patients have the potential to benefit from treatment with a PARP inhibitor.

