7.5 Post-treatment Phase

7.5.1 End of Treatment Visit

Upon treatment discontinuation, regardless of the reason, patients will have an End of Treatment Visit. For patients that have radiologic disease progression by RECIST v1.1, but continue to derive benefit in the opinion of the investigator, they will be allowed to continue treatment in the Treatment Phase. In such cases, the investigator's decision to continue treatment should be documented in the source documents and the patient must provide additional consent prior to continuing treatment with rucaparib as described starting in [Section 7.4.5](#) and an End of Treatment Visit will occur at the end of all rucaparib treatment. Patients who continue treatment with rucaparib after radiologic disease progression will have the option of tumor tissue biopsy collection at time of first disease progression on study (requires additional consent). Tumor tissue will be processed locally as FFPE tissue. Refer to the Pathology Charter for detailed sample handling instructions.

The following procedures will be performed at the End of Treatment Visit:

- Physical examination
- Weight
- ECOG performance status ([Appendix 2](#))
- Vital signs
- Concomitant medications and any surgical/medical procedures
- 12-lead ECG
- Tumor assessment/ scans if it has been ≥ 8 weeks since the last assessment
- Hematology
- Serum chemistry (fasting is not required)
- Urinalysis
- Serum pregnancy test for women of childbearing potential
- Collect ctDNA blood sample
- AE monitoring
- Patients return all unused tablets and containers (empty, partially used, and/or unopened) to the study site for final accountability.
- Optional tumor tissue biopsy collection after the time of disease progression (radiologic or clinical) and prior to initiation of any subsequent anti-cancer therapy (requires additional consent). Tumor tissue will be processed locally as FFPE tissue. Refer to the Pathology Charter for detailed sample handling instructions.

7.5.2 28-day Follow-up Visit

The following procedures will be performed for all patients at 28 (± 3) days after the last dose of rucaparib.

- Physical examination
- Weight
- ECOG performance status ([Appendix 2](#))
- Vital signs
- Concomitant medications and any surgical/medical procedures
- Tumor assessment only for those patients that have not had radiographic progression confirmed by investigator assessment
- Hematology
- Serum chemistry (fasting is not required)
- Urinalysis

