9.5.2.2 Progression-free Survival

Progression-free survival (PFS) will be calculated as 1+ the number of days from the first dose of rucaparib to disease progression or death due to any cause, whichever occurs first. Patients without a documented event of progression will be censored on the date of their last adequate tumor assessment (ie, radiologic assessment) or date of first dose of rucaparib if no post-baseline tumor assessments have been performed.

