10 PATIENT DISPOSITION

10.1 Removal of Patients from the Study or Study Drug

A patient must be discontinued from protocol prescribed therapy if any of the following apply:

- Consent withdrawal for any reason at the patient's own request or at the request of their legally authorized representative (where acceptable according to national law and/or local regulations);
- Radiographic progression of patient's underlying cancer per RECIST v1.1 (unless, in the opinion of the investigator, the patient continues to derive clinical benefit; treatment beyond progression is permitted with additional consent);
- Unequivocal clinical progression of the patient's underlying cancer that, in the opinion of the investigator, requires immediate change in systemic anti-cancer therapy, or results in marked deterioration in ECOG performance status to Grade 3 or higher
- Any event, adverse or otherwise, that, in the opinion of the investigator, would pose an unacceptable safety risk to the patient;
- An intercurrent illness that, in the opinion of the investigator, would affect assessments of the clinical status to a significant degree and requires discontinuation of therapy; or
- Noncompliance by the patient with protocol mandated procedures.

Discontinuation of treatment does not necessarily indicate study discontinuation for a patient. Samples collected for research will continue to be used unless the patient explicitly withdraws consent for their use. If the patient withdraws consent to continue in the study or discontinues the study for another reason it will be documented on the appropriate eCRF. A patient may withdraw consent to participate in an additional part of a study that has an additional consent (ie, optional tumor biopsy) yet continue to participate and be treated/ followed in the main part of the study.

The sponsor may discontinue the study early for any of the reasons noted in [Section 11.7](#).

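### PFS censors patients who switch therapy for clinical progression at an earlier scan or at first dose; this biases the single-arm estimate upward, and no sensitivity analysis is planned

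*SAP*

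**What the plan says.** **Event.** SAP 9.2.2 runs PFS from first dose to the "date of first objective evidence of progression documented by the investigator per RECIST v1.1 or death due to any cause". Clinical progression is not an event.

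**Censoring at new therapy.** The same section begins the rule with "If a patient discontinues study drug due to something other than PD" and continues: if that patient "begins another anti-cancer therapy (ACT) prior to a PFS, that patient will be censored at the last tumor scan prior to the start of ACT". Without a scan, censoring is at the "date of first dose of study drug if no tumor scans have been performed". Protocol 9.5.2.2 is clearer on that last point ("date of first dose of rucaparib if no post-baseline tumor assessments have been performed") but has neither the new-therapy rule nor the 90-day rule that follows it in the SAP.

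**Clinical progression.** Protocol 10.1 lists it separately from radiographic progression. One limb is progression that "requires immediate change in systemic anti-cancer therapy"; the other is marked decline in ECOG status. The RECIST summaries appended to both documents class general deterioration without objective evidence as symptomatic deterioration, not PD.

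**Scans.** Scans are every 8 weeks (±7 days) from Cycle 1 Day 1. At the End of Treatment Visit (Protocol 7.5.1) the requirement is "Tumor assessment/ scans if it has been ≥ 8 weeks since the last assessment". The 28-day visit has a scan for patients without radiographic progression. Protocol Table 5 and Section 7.5.3 end off-treatment scans when new treatment starts.

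**Sensitivity analyses of PFS.** Neither document plans one.

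**The concern.** Kaplan-Meier estimation needs patients censored at a given time to have the same outlook as those who stay at risk. Here a patient leaves the risk set because the cancer has worsened enough to force a change of treatment, and the exit is back-dated to a scan taken before the worsening. That is informative censoring, and its direction is known: failures become censored observations, so the curve sits too high.

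The early part of the curve is the most exposed. Protocol 1.4 states that "the majority of patients will progress within 2 to 3 months following failure on first- and/or second-line therapy", while the first on-study scan is not due until week 8. Estimating PFS is a named secondary objective, and SAP 9.3 allows PFS as an endpoint in the HRD subgroups. With one arm, no comparator shares the bias.

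**Working it through.** **The plan's own figure.** No figure is given for PFS. The only power statement concerns ORR. The rule Pr(p > 0.10 | data) > 0.95 with a Beta(0.1, 0.9) prior needs at least 28 of 200 responses. Exact binomial tails give type I error 0.0434 at p = 0.10 and power 0.9890 at p = 0.20, matching the Fixed row (0.043, 0.989). The PFS rule does not enter this calculation.

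**Inputs from the documents.** N = 200; scans every 56 days ±7; progression time 2 to 3 months; screening scan up to 28 days before dosing.

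**Assumptions.** Time to progression or death is exponential with median m = 2, 2.5 or 3 months. Deaths, dated exactly, are 10% of events. Clinical progression followed by new therapy before a scan shows PD is a share c = 10%, 20% or 30% of events. The documents give no value for c.

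**Share censored at Day 1.** With no scan before week 8, the share is P(T < 56 days) = 1 − 2^(−1.84/m), where 1.84 = 56/30.4375 months.
- m = 2: 47.1%; m = 2.5: 40.0%; m = 3: 34.6%.

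The End of Treatment scan can count its 8 weeks from the screening scan. If screening was 14 days before dosing, that scan is due from day 42 (1.38 months), and the share becomes 38.0%, 31.8% and 27.3%. If every screening scan were at Day −28, it would be due from day 28 (0.92 months): 27.3%, 22.5% and 19.1%. After the week-8 scan, a patient on schedule has almost no interval in which the End of Treatment scan is due before the next planned one, so it helps mainly in the first interval.

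At c = 20%, 40 of 200 patients are affected. Day-1 censoring is 40 × 0.346 to 40 × 0.471, about 14 to 19 patients. With screening 14 days before dosing it is 40 × 0.273 to 40 × 0.380, about 11 to 15.

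**Effect on 26-week PFS.** Kaplan-Meier on 400,000 simulated patients per scenario. *Event*: clinical progression counted on its date. *SAP*: censored at the last scan, or Day 1 if none. *SAP + EOT*: as SAP, but an End of Treatment scan due before week 8 records PD, with screening scans spread evenly over Day −28 to −1.

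| m (months) | c | Event | SAP | SAP + EOT | Overstatement, points (SAP; SAP + EOT) |
|---|---|---|---|---|---|
| 2 | 10% | 14.3% | 16.2% | 16.0% | 1.9; 1.7 |
| 2 | 20% | 14.1% | 18.3% | 17.9% | 4.2; 3.7 |
| 2 | 30% | 14.0% | 20.9% | 20.2% | 7.0; 6.2 |
| 2.5 | 10% | 21.2% | 23.6% | 23.4% | 2.4; 2.2 |
| 2.5 | 20% | 21.0% | 26.3% | 25.8% | 5.4; 4.8 |
| 2.5 | 30% | 20.6% | 29.4% | 28.5% | 8.8; 7.9 |
| 3 | 10% | 27.4% | 30.2% | 30.0% | 2.8; 2.6 |
| 3 | 20% | 27.1% | 33.1% | 32.5% | 6.1; 5.5 |
| 3 | 30% | 26.9% | 36.8% | 35.8% | 9.9; 8.9 |

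(Differences were taken before rounding.) A simpler model without deaths gives 6-month gaps of 2.5 to 11.7 points. The direction is upward in every scenario.

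**Medians.** At m = 2.5 and c = 30%, the median is about 3.8 months as written against 3.5. At m = 3 and c = 30%, repeat simulations of the as-written median ranged from 4.3 to 5.4 months against 3.7, and it falls to about 3.9 in most runs with the End of Treatment scan. The curve drops in steps near scan dates, so a small shift can move the median a whole interval. Landmark PFS is the usable measure.

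**The case against.** Much of the opposing case stands.

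- **Convention.** Censoring at new therapy with a RECIST-only event is common. That justifies keeping the analysis, but not having it as the only one.
- **Safeguards.** The End of Treatment scan, the 28-day scan and the appendix's request to document objective progression can all capture PD. Patients who start no new therapy and die within 90 days of stopping count as events. These limit the bias but do not remove it: a scan helps only if it precedes the new therapy, and this group is defined by an urgent switch. Some Protocol sentences (3.1.3, 7.6.3) omit new treatment as a reason to stop scanning, but the SAP censors before new therapy, so later scans cannot restore the event.
- **Scope.** The SAP does not say whether clinical progression counts as PD in this rule. If it does, the new-therapy sentence does not apply. The general rule still censors at the last adequate scan or first dose, unless a later scan or death supplies an event, and that event is later than the clinical progression. The bias remains upward.
- **Size.** The share c has no anchor, and treatment options after platinum and checkpoint inhibitors are described as limited, so switching may be rare. At c = 10% and m = 2.5 the gap of 2.4 points is below one standard error at N = 200: √(0.21 × 0.79/200) = 2.9 points.
- **Existing outputs.** SAP 3 displays events and censored patients over time, and SAP 4 summarises reasons for discontinuation. They are not cross-classified, so the reader could not see how many were censored for worsening disease.

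A reader might also infer that the plan will set this curve against the 2-to-3-month historical figure. The documents do not say so: that figure is background, and the only performance goal is an ORR of 10%.

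**Conclusion.** The concern holds. Patients who stop for unequivocal clinical progression and switch before a scan shows PD are censored because their disease worsened, and single-arm PFS is biased upward. With c = 10–30% and a true median of 2–3 months, 26-week PFS is overstated by about 2 to 10 percentage points, or about 2 to 9 with the End of Treatment scan modelled. These figures rest on the assumed share, exponential times and 10% of events as deaths. The 28-day scan was not modelled; any PD it finds before new therapy would reduce them.

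Two stronger readings are tempting. One is that most affected patients are censored at Day 1; the calculation gives about 27–47%, a substantial minority, and less if screening scans are early. The other is that median PFS is inflated by a month or more; that shift is unstable on the 8-week grid and should not be quoted.

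The primary ORR is unaffected. PFS is a descriptive secondary endpoint with no test or decision rule. Priority: low to moderate.

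**What to change.** In SAP 9.2.2:

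1. Keep the current PFS analysis.
2. State whether PD in the new-therapy rule includes unequivocal clinical progression.
3. Add one prespecified sensitivity Kaplan-Meier analysis. Investigator-declared unequivocal clinical progression, without prior RECIST PD or death, counts as an event on the date of the discontinuation decision. New therapy started after toxicity or another non-progression reason stays censored; counting every switch as an event would bias PFS downward.
4. Report the numbers censored at Day 1 and censored for new therapy, by reason for discontinuation.
5. Present both curves side by side, without choosing between them after seeing the data.

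The date and reason for stopping rucaparib (Protocol 3.1.3) and subsequent treatments (Protocol 7.5.3) are already collected, and no trial procedure changes. The cost is SAP wording, one extra analysis and one table. The downsides are a PFS figure that may be less favourable and reliance on an investigator-judged event in an open-label trial, which is why it belongs in a sensitivity analysis.

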3.1.3 Post-treatment Phase

The sponsor or designee should be notified of all treatment terminations as soon as possible. The date and reason for cessation of rucaparib must be documented in the eCRF and source documents. Patients will undergo procedures and assessments during the Post-treatment Phase as described in [Section 7.5](#). Upon treatment discontinuation, patients will have an End of Treatment Visit ([Section 7.5.1](#)), a 28-day Follow-up Visit ([Section 7.5.2](#)), and then will proceed to long-term follow-up ([Section 7.5.3](#)).

All patients enrolled into the study will provide an End of Treatment Visit blood sample for ctDNA analysis. An optional tumor biopsy will be collected prior to the start of subsequent anti-cancer therapy from patients who experience radiographic or unequivocal clinical disease progression and who provide additional consent.

For patients who had their last tumor assessment ≥ 8 weeks prior to End of Treatment Visit, a tumor assessment must be performed.

If treatment was discontinued for reasons other than radiologic disease progression or death, radiologic tumor assessment (using the same methodology as was used at initial study screening [eg, CT scan]) will continue until confirmed radiographic disease progression by RECIST v1.1 criteria as assessed by the investigator, loss to follow-up, withdrawal of consent, death, initiation of subsequent treatment, or study closure. For these patients, tumor assessments should continue to be performed at the end of every 8 calendar weeks (± 7 days) relative to Cycle 1 Day 1 up to 18 months and then every 12 calendar weeks (± 7 days) thereafter, until confirmed radiologic disease progression by RECIST v1.1 criteria as assessed by the investigator, loss to follow-up, withdrawal of consent, death, or study closure.

[figure not shown]
Ongoing serious adverse events (SAEs), AESIs, and treatment-related Grade 3/4 AEs will be followed until either resolution or stabilization has been determined or until loss to follow-up. After the 28-day Follow-up Visit, related SAEs and all AESIs (irrespective of causality) need to be reported.

All patients will be followed for survival and subsequent treatments every 12 weeks (± 14 days) relative to the last dose of rucaparib until death, loss to follow-up, withdrawal of consent, or study closure.

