7.5.3 Long-term Follow-up

Patients who complete a 28-day Follow-up Visit after the last dose of rucaparib will continue in long-term follow-up as described below.

- If applicable, tumor assessment (using the same methodology as was used at initial study screening [eg, CT scan or MRI scan if required by local authorities]) when the reason for treatment discontinuation was other than death or disease progression based on radiologic assessment and it has been ≥ 8 weeks since last scan or disease progression was noted on the last scan. Tumor assessment should continue to be performed at the end of every 8 calendar weeks (± 7 days) relative to Cycle 1 Day 1 up to 18 months, then every 12 calendar weeks (± 7 days), until confirmed radiologic disease progression by RECIST v1.1 criteria as assessed by the investigator, loss to follow-up, withdrawal, death, initiation of subsequent treatment, or study closure.
- All patients discontinued from treatment, regardless of reason, will be followed and information collected for subsequent treatments and survival every 12 weeks from last dose of rucaparib until death, loss to follow-up, withdrawal of consent from study, or closure of the study. Follow-up can be performed via the telephone and can be completed to coincide with scheduled tumor assessments.
- SAEs related to rucaparib and all AESIs, irrespective of causality, are to be reported as specified in [Section 8.9](#).

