9 PLANNED STATISTICAL METHODS

9.1 General Considerations

Quantitative variables will typically be summarized using frequencies and percentages for appropriate categorizations and may also be summarized using descriptive statistics. For variables summarized with descriptive statistics, the following will be presented: N, mean, standard deviation (StD), median, minimum, and maximum. Categorical variables will be presented using frequencies and percentages.

The Kaplan-Meier methodology will be used to summarize time-to-event variables. If estimable, the 25th, 50th (median), and 75th percentiles with the 95% confidence interval (CI) will be summarized. The number of patients with events and the number of censored patients will also be presented.

All data will be used to their maximum possible extent, but without any imputations for missing data. Unless otherwise specified, baseline is defined as the last measurement on or prior to the first day of rucaparib administration.

All statistical analyses will be conducted with the SAS[®] System, Version 9.3 or higher. Further details regarding the statistical analyses planned in this study will be outlined in the SAP.

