9.2 Secondary Efficacy Analyses

9.2.1 Duration of Confirmed Response

The duration of confirmed response is defined as the time from the date that a response is first documented per RECIST v1.1 by the investigator to the time that progression is first documented per RECIST v1.1 by the investigator, plus 1 day.

The duration of confirmed response will be analyzed and summarized in a Kaplan-Meier plot. Any patient with an ongoing response at the time of data cut-off for analysis will be censored at the date of the last post-baseline scan. In the case of a low censoring rate, the duration of response may be summarized with descriptive statistics.

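### SAP 9.2.2 drops PFS events more than 90 days after rucaparib is stopped, although the protocol counts them, and moves back only the patients who have the event

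*SAP*

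**What the plan says.** Protocol 9.5.2.2 measures PFS "from the first dose of rucaparib to disease progression or death due to any cause, whichever occurs first". Its only censoring rule is "Patients without a documented event of progression will be censored on the date of their last adequate tumor assessment", or the first-dose date if there is no post-baseline assessment. It sets no window after treatment ends and has no rule for new therapy.

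SAP 9.2.2 begins with the same event definition, which also stands in the SAP's endpoint table (Section 2.2). It then adds two rules. A patient who stops for a reason other than progression and starts another anti-cancer therapy (ACT) before an event is censored at the last scan before ACT. The next sentence says that "PFS events occurring more than 90 days after discontinuation of study drug, but prior to start of subsequent ACT, will not be included in" this analysis; patients with such events are censored at the last scan before the 90-day window closes.

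The protocol continues to collect what this rule discards. After a stop without progression, the 28-day visit (Protocol 7.5.2) includes "Tumor assessment only for those patients that have not had radiographic progression confirmed by investigator assessment". In long-term follow-up (7.5.3), "Tumor assessment should continue to be performed at the end of every 8 calendar weeks" up to 18 months, and every 12 weeks after that. Section 3.1.3 adds: "All patients will be followed for survival and subsequent treatments every 12 weeks".

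SAP 9.2.1 ends duration of response (DOR) with the words "to the time that progression is first documented per RECIST v1.1 by the investigator, plus 1 day", and has no 90-day limit.

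**The concern.** The rule changes which events count as PFS events. Protocol 9.1 says "Further details regarding the statistical analyses planned in this study will be outlined in the SAP", but removing events that the protocol counts is more than a detail. SAP Sections 1 to 13 do not declare it as a change from the protocol, give no reason for it, and plan no analysis without it.

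The rule also works in one direction only. Time since stopping drug triggers it, but only in patients who go on to have an event. A patient who stopped drug and is still event-free beyond day 90 is followed to the last adequate scan. Past the window, therefore, stopped patients remain in the risk set only if no event has been recorded for them before new therapy or cut-off. Kaplan-Meier estimation assumes that censoring carries no information about the outcome, and here the outcome decides the censoring.

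At stake are the PFS curve and the landmark rates. SAP 9.3 also allows this PFS in the exploratory HRD subgroup analyses, including those across LOH cutpoints (9.3.1).

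**Working it through.** The documents give no PFS event target, power or expected curve, so there is no figure of the plan's own to reproduce. The check has three parts.

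**1. One patient, from the stated rules.** Days are counted from first dose and scans fall every 56 days. The patient responds on day 56, stops for a reason other than progression on day 120, has the 28-day scan on day 148, progresses on the day-280 scan, and receives no ACT.

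- Window closes: 120 + 90 = day 210. Scans before that: 56, 112, 148, 168. The last is day 168.

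| Measure | Calculation | Result |
|---|---|---|
| Protocol PFS | 280 + 1 | event at 281 days |
| SAP PFS | 168 + 1 | censored at 169 days |
| SAP PFS, same patient, event-free on the day-280 scan | 280 + 1 | censored at 281 days |
| SAP DOR | 280 - 56 + 1 | event at 225 days |

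The progression itself removes 112 days of follow-up (281 - 169) from PFS, yet it still counts as an event for DOR.

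**2. Size in 200 patients, by simulation.** Only the time scale has a source: the protocol's Rationale says most patients progress within 2 to 3 months of starting treatment for relapsed disease. Everything else is assumed.

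- Median PFS 2.5, 3 or 4 months; event and stopping times exponential.
- 20% or 30% of patients stop for a reason other than progression; hazard after stopping 0.5, 1 or 1.5 times the hazard before.
- 20% of events are deaths, dated exactly. Progression is dated to the next scan (every 56 days to day 560, then every 84, plus one 28 days after stopping).
- 0%, 50% or 70% of those who stop start ACT, evenly over days 0-90. Data cut-off is uniform over 4-30 months.
- 3 x 2 x 3 x 3 = 54 scenarios, 400,000 patients each.

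The Kaplan-Meier estimate, the product of (1 - events / number at risk) over event times, was computed with and without the 90-day sentence. ACT censoring was kept in both.

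| ACT uptake | Events lost per 200 | 6-month PFS shift (points) | 12-month PFS shift (points) |
|---|---|---|---|
| 50-70% | 4.2 to 15.0 | -0.7 to +0.5 | -0.3 to +1.4 |
| 0% | 13.9 to 30.1 | -0.8 to +0.9 | +0.1 to +2.3 |

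Examples with a 4-month median, 30% stopping and no ACT:

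- Hazard 1.5: 6-month PFS 34.9% to 35.8% (+0.9); 12-month 10.9% to 13.2% (+2.3).
- Hazard 0.5: 6-month PFS 41.7% to 41.5% (-0.2).

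The sign can change because two effects compete. Back-dating shrinks the risk set between the window and the event, which lowers the curve. Dropping the event afterwards raises it. With no ACT, the 6-month shift is -0.8 to -0.2 at hazard 0.5, +0.1 to +0.4 at 1, and +0.5 to +0.9 at 1.5.

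The median moved by about 2 days at most, and by about 3 days in a separate run of the hazard-1.5 example. With deaths at 10% or 40% of events the ranges widen to -1.2 to +1.1 points at 6 months, -0.3 to +2.5 at 12 months, and about 6 days either way for the median.

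**3. Sensitivity to heavier stopping and later ACT.** A second simulation (400,000 patients per scenario) used progression only and an unchanged hazard after stopping. Medians were 2.5, 4 and 6 months, stopping was 10-40% of the combined hazard, ACT was never started or started at a median of 6 months after stopping, and cut-off was at 6-18 months. Hazards were ln 2 / (median x 30.44 days) for progression and that value times d / (1 - d) for stopping share d. The SAP rule removed about 2-19% of events. It raised 6-month PFS by about 0.2-2 points and 12-month PFS by about 0.4-7 points, upward in every scenario. At a 4-month median, d = 40% and no ACT, 12-month PFS was 14.8% under the protocol rule and 21.7% under the SAP rule. The median did not move.

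**The case against.** **It hardly matters.** The objective is to estimate PFS, with no test, comparator or decision rule. At n = 200, ignoring censoring, the standard error is sqrt(0.35 x 0.65 / 200) = 3.4 points at 35% PFS and sqrt(0.11 x 0.89 / 200) = 2.2 points at 11%. With 50-70% ACT uptake the shift is below one standard error and its sign varies. This stands, and it keeps the point well below a threat to the trial's conclusions. It does not justify reporting an endpoint other than the one defined.

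**The size is uncertain.** This also stands. The ACT uptake has no source; Protocol 10.1 shows only that clinical progression needing a change of therapy is one reason to stop. The no-ACT row is not an upper bound, because it holds for 20-30% stopping. Separate runs at 40% stopping without ACT lost about 29-41 events per 200, with 12-month shifts of up to +4.7 points. This means the table may understate the effect.

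**The rule is openly written, and the SAP may supply details.** True. The SAP's front matter was not available, so the statement that the change is undeclared is limited to Sections 1 to 13.

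**A narrower reading.** The sentence follows the ACT rule and opens with a contrasting word, so it could be meant only for patients who later start ACT. The text does not say so, and the broader reading is the more natural. If the narrow meaning is intended, it needs stating.

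**A symmetric window would also remove the outcome dependence.** Censoring every stopped patient at 90 days does so, and in the second simulation it agreed with the protocol curve. It is not bias-free when the hazard changes after stopping: at hazard 0.5 it moved 12-month PFS by up to -4.7 points.

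**Conclusion.** The concern holds. SAP 9.2.2 contradicts Protocol 9.5.2.2, and its own opening sentence, on which events count, and it applies the exclusion only to patients who have the event. Neither conclusion needs an assumption, apart from the natural reading of the sentence.

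The size does need assumptions. It is modest at 20-30% stopping and grows with heavier stopping or later ACT; the direction depends on the hazard after stopping. Only patients who stop for a reason other than radiologic progression, and have their event more than 90 days later without new therapy, are affected. The landmark rates and the tail of the curve are exposed, the median hardly at all. Response rate, overall survival, power and the interim rules do not change. The DOR contrast is inconsistent handling, not a contrary instruction. The sentence should be corrected before analysis.

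**What to change.** - Delete the 90-day sentence from the main PFS analysis in SAP 9.2.2, so that every progression or death before subsequent ACT counts.
- If a 90-day version is wanted, keep it as a labelled sensitivity analysis with its reason, and say whether the window applies to all stopped patients or only to those with an event.
- State in SAP 9.2.2 that censoring at subsequent ACT is an addition to Protocol 9.5.2.2. This removes the 90-day mismatch with DOR but does not fully align the two, since SAP 9.2.1 has no ACT or death rule.
- Separate wording point: in both documents, the censoring sentence should cover patients with neither progression nor death. Read literally, it also censors a patient who dies without documented progression.

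The cost is one SAP sentence deleted or moved, one statement added, and a one-line clarification in each document. No new data are needed.
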